Appendix C Handling of Human Biological Samples

C 1 Chain of Custody

A full chain of custody is maintained for all samples throughout their lifecycle.

The investigator at each center keeps full traceability of collected biological samples from the participants while in storage at the center until shipment or disposal (where appropriate) and records relevant processing information related to the samples while at site.

The sample receiver keeps full traceability of the samples while in storage and during use until used or disposed of or until further shipment and keeps record of receipt of arrival and onward shipment or disposal.

The sponsor or delegated representatives will keep oversight of the entire lifecycle through internal procedures, monitoring of study sites, auditing or process checks, and contractual requirements of external laboratory providers

Samples retained for further use will be stored in the sponsor's assigned biobanks or other sample archive facilities and will be tracked by the appropriate staff during for the remainder of the sample lifecycle.

If required, the sponsor will ensure that remaining biological samples are returned to the site according to local regulations or at the end of the retention period, whichever is the sooner.

C 2 Withdrawal of Informed Consent for Donated Biological Samples

If a participant withdraws consent to the use of donated biological samples, the samples will be disposed of/destroyed/repatriated, and the action documented. If samples have already been analyzed, the sponsor is not obliged to destroy the results of the research.

Following withdrawal of consent for biological samples, further study participation should be considered in relation to the withdrawal processes outlined in the informed consent.

The investigator:

- Ensures participant's withdrawal of informed consent to the use of donated samples is highlighted immediately to the sponsor or delegate
- Ensures that relevant human biological samples from that participant, if stored at the study site, are identified immediately, disposed of appropriately, and that the action is documented
- Ensures that the participant and the sponsor are informed about the sample disposal

The sponsor ensures the organization(s) holding the samples is/are informed about the withdrawn consent immediately, and that samples are disposed of or repatriated as appropriate, and that the action is documented and study site is notified.

C 3 International Airline Transportation Association (IATA) 6.2 Guidance Document

LABELING AND SHIPMENT OF BIOHAZARD SAMPLES

IATA (<https://www.iata.org/whatwedo/cargo/dgr/Pages/download.aspx>) classifies infectious substances into 3 categories: Category A, Category B or Exempt

Category A Infectious Substances are infectious substances in a form that, when exposure to it occurs, is capable of causing permanent disability, life-threatening or fatal disease in otherwise healthy humans or animals.

Category A pathogens are, eg, Ebola, Lassa fever virus. Infectious substances meeting these criteria which cause disease in humans or both in humans and animals must be assigned to UN 2814. Infectious substances which cause disease only in animals must be assigned to UN 2900.

Category B Infectious Substances are infectious substances that do not meet the criteria for inclusion in Category A. Category B pathogens are, eg, Hepatitis A, C, D, and E viruses. They are assigned the following UN number and proper shipping name.

- UN 3373 – Biological Substance, Category B
- are to be packed in accordance with UN3373 and IATA 650

Exempt - Substances which do not contain infectious substances or substances which are unlikely to cause disease in humans or animals are not subject to these Regulations unless they meet the criteria for inclusion in another class.

- Clinical study samples will fall into Category B or exempt under IATA regulations
- Clinical study samples will routinely be packed and transported at ambient temperature in IATA 650 compliant packaging (<https://www.iata.org/whatwedo/cargo/dgr/Documents/DGR-60-EN-PI650.pdf>).
- Biological samples transported in dry ice require additional dangerous goods specification for the dry ice content

Appendix D Optional Genomics Initiative Sample

D 1 Use/Analysis of DNA

- The sponsor intends to collect and store DNA for genetic research to explore how genetic variations may affect clinical parameters, risk and prognosis of diseases, and the response to medications. This genetic research may lead to better understanding of diseases, better diagnosis of diseases or other improvements in healthcare and to the discovery of new diagnostics, treatments or medications. Therefore, where local regulations and IRB/IEC allow, a blood sample will be collected for DNA analysis from consenting participants.
- This optional genetic research may consist of the analysis of the structure of the participant's DNA, ie, the entire genome.
- The results of genetic analyses may be reported in a separate study summary.
- The sponsor will store the DNA samples in a secure storage space with adequate measures to protect confidentiality.
- The samples will be retained for up to 15 years after the end of the study.

D 2 Genetic Research Plan and Procedures

Selection of Genetic Research Population

All participants will be asked to participate in this genetic research. Participation is voluntary and if a participant declines to participate there will be no penalty or loss of benefit. The participant will not be excluded from any aspect of the main study.

Inclusion Criteria

For inclusion in this genetic research, participants must fulfill all of the inclusion criteria described in Section 5.1 and provide informed consent for the Genomics Initiative sampling and analyses.

Exclusion Criteria

Exclusion from this genetic research may be for any of the exclusion criteria specified in the main study or any of the following:

- Previous allogeneic bone marrow transplant
- Non-leukocyte depleted whole blood transfusion in 120 days of genetic sample collection

Withdrawal of Consent for Genetic Research

- Participants may withdraw from this genetic research at any time, independent of any decision concerning participation in other aspects of the main study. Voluntary withdrawal will not prejudice further treatment. Procedures for withdrawal are outlined in Section 7.2.

Collection of Samples for Genetic Research

The blood sample for this genetic research will be obtained from the participants at Day 1, Visit 3 (before dosing). Although DNA is stable, early sample collection is preferred to avoid introducing bias through excluding participants who may withdraw due to an AE. If for any reason the sample is not drawn at Day 1, Visit 3, it may be taken at any visit until the last study visit. Only one sample should be collected per participant for genetics during the study.

Coding and Storage of DNA Samples

- The processes adopted for the coding and storage of samples for genetic analysis are important to maintain participant confidentiality. Samples will be stored for a maximum of 15 years from the date of last participant last visit, after which they will be destroyed. DNA is a finite resource that is used up during analyses. Samples will be stored and used until no further analyses are possible or the maximum storage time has been reached.
- An additional second code will be assigned to the sample either before or at the time of DNA extraction replacing the information on the sample tube. Thereafter, the sample will be identifiable only by the second, unique number. This number is used to identify the sample and corresponding data at the sponsor's genetics laboratories, or at the designated organization. No personal details identifying the individual will be available to any person (sponsor employee or designated organizations working with the DNA).
- The link between the participant enrollment/randomization code and the second number will be maintained and stored in a secure environment, with restricted access at sponsor or designated organizations. The link will be used to identify the relevant DNA samples for analysis, facilitate correlation of genotypic results with clinical data, allow regulatory audit, and permit tracing of samples for destruction in the case of withdrawal of consent.

Ethical and Regulatory Requirements

The principles for ethical and regulatory requirements for the study, including this genetics research component, are outlined in [Appendix A](#).

Informed Consent

The genetic component of this study is optional and the participant may participate in other components of the main study without participating in this genetic component. To participate in the genetic component of the study, the participant must sign and date both the consent form for the main study and the addendum for the Genomics Initiative component of the study. Copies of both signed and dated consent forms must be given to the participant and the original filed at the study center. The Principal investigator(s) is responsible for ensuring that consent is given freely and that the participant understands that they may freely withdraw from the genetic aspect of the study at any time.

Participant Data Protection

- The sponsor will not provide individual genotype results to participants, any insurance company, any employer, their family members, or general physician unless required to do so by law.
- Extra precautions are taken to preserve confidentiality and prevent genetic data being linked to the identity of the participant. In exceptional circumstances, however, certain individuals might see both the genetic data and the personal identifiers of a participant. For example, in the case of a medical emergency, a sponsor physician or an investigator might know a participant's identity and also have access to his or her genetic data. Regulatory authorities may require access to the relevant files, though the participant's medical information and the genetic files would remain physically separate.

Data Management

- Any genetic data generated in this study will be stored at a secure system by the sponsor and/or designated organizations to analyze the samples.
- The sponsor and its designated organizations may share summary results (such as genetic differences from groups of individuals with a disease) from this genetic research with other researchers, such as hospitals, academic organizations or health insurance companies. This can be done by placing the results in scientific databases, where they can be combined with the results of similar studies to learn even more about health and disease. The researchers can only use this information for health-related research purposes. Researchers may see summary results but they will not be able to see individual participant data or any personal identifiers.
- Some or all of the clinical datasets from the main study may be merged with the genetic data in a suitable secure environment separate from the clinical database.

Appendix E Actions Required in Cases of Increases in Liver Biochemistry and Evaluation of Hy's Law

E 1 Introduction

This appendix describes the process to be followed in order to identify and appropriately report Potential Hy's Law cases and Hy's Law cases. It is not intended to be a comprehensive guide to the management of elevated liver biochemistries.

Specific guidance on managing liver abnormalities can be found in Section [8.3.6](#).

During the study the investigator will remain vigilant for increases in liver biochemistry. The investigator is responsible for determining whether a participant meets potential Potential Hy's Law criteria at any point during the study.

All sources of laboratory data are appropriate for the determination of Potential Hy's Law and Hy's Law events; this includes samples taken at scheduled study visits and other visits including central and all local laboratory evaluations even if collected outside of the study visits; for example, Potential Hy's Law criteria could be met by an elevated ALT from a central laboratory **and/or** elevated TBL from a local laboratory.

The investigator will also review AE data (for example, for AEs that may indicate elevations in liver biochemistry) for possible Potential Hy's Law events.

The investigator participates, together with the sponsor's clinical project representatives, in review and assessment of cases meeting Potential Hy's Law criteria to agree whether Hy's Law criteria are met. HL criteria are met if there is no alternative explanation for the elevations in liver biochemistry other than DILI caused by the investigational product.

The investigator is responsible for recording data pertaining to Potential Hy's Law/Hy's Law cases and for reporting SAEs and AEs according to the outcome of the review and assessment in line with standard safety reporting processes.

E 2 Definitions

Potential Hy's Law

AST or ALT $\geq 3x$ ULN **together with** TBL $\geq 2x$ ULN at any point during the study following the start of study medication irrespective of an increase in ALP.

Hy's Law

AST or ALT $\geq 3x$ ULN **together with** TBL $\geq 2x$ ULN, where no other reason, other than the investigational product, can be found to explain the combination of increases, eg, elevated ALP indicating cholestasis, viral hepatitis, another drug.

For Potential Hy's Law and Hy's Law, the elevation in transaminases must precede or be coincident with (ie, on the same day) the elevation in TBL, but there is no specified timeframe within which the elevations in transaminases and TBL must occur.

E 3 Identification of Potential Hy's Law Cases

In order to identify cases of Potential Hy's Law, it is important to perform a comprehensive review of laboratory data for any participant who meets any of the following identification criteria in isolation or in combination:

- ALT \geq 3x ULN
- AST \geq 3x ULN
- TBL \geq 2x ULN

Central Laboratories Being Used:

When a participant meets any of the Potential Hy's Law identification criteria, in isolation or in combination, the central laboratory will immediately send an alert to the investigator (also sent to the sponsor's representative).

The investigator will also remain vigilant for any local laboratory reports where the Potential Hy's Law identification criteria are met; where this is the case, the investigator will:

- Notify the sponsor's representative.
- Request a repeat of the test (new blood draw) by the central laboratory without delay.
- Complete the appropriate unscheduled laboratory eCRF module(s) with the original local laboratory test result.

When the identification criteria are met from central or local laboratory results, the investigator will without delay:

- Determine whether the participant meets Potential Hy's Law criteria (refer to Appendix [E 2](#) for definition) by reviewing laboratory reports from all previous visits (including both central and local laboratory results).

Local Laboratories Being Used:

The investigator will without delay review each new laboratory report and if the identification criteria are met will:

- Notify the sponsor's representative.
- Determine whether the participant meets Potential Hy's Law criteria (refer to Appendix [E 2](#) for definition) by reviewing laboratory reports from all previous visits.
- Promptly enter the laboratory data into the laboratory eCRF.

E 4 Follow-up

E 4.1 Potential Hy's Law Criteria Not Met

If the participant does not meet Potential Hy's Law criteria the investigator will:

- Inform the sponsor's representative that the participant has not met Potential Hy's Law criteria.
- Perform follow-up on subsequent laboratory results according to the guidance provided in the CSP.

E 4.2 Potential Hy's Law Criteria Met

If the participant does meet Potential Hy's Law criteria the investigator will:

- Determine whether Potential Hy's Law criteria were met at any study visit before starting study treatment (refer to Section 8.3.6).
- Notify the sponsor's representative who will then inform the central Study Team
- Within 1 day of Potential Hy's Law criteria being met, the investigator will report the case as an SAE of Potential Hy's Law; serious criteria 'Important Medical Event' and causality assessment 'yes/related' according to CSP process for SAE reporting.
- For participants that met Potential Hy's Law criteria before starting the study intervention, the investigator is not required to submit a Potential Hy's Law SAE unless there is a significant change¹ in the participant's condition.
- The Study Physician contacts the investigator to provide guidance, discuss, and agree on an approach for the study participants' follow-up (including any further laboratory testing) and the continuous review of data
- After this contact, the investigator will:
 - Monitor the participant until liver biochemistry parameters and appropriate clinical symptoms and signs return to normal or baseline levels, or as long as medically indicated. Complete follow-up SAE Form as required.
 - Investigate the etiology of the event and perform diagnostic investigations as discussed with the Study Physician. This includes deciding which of the tests available in the Hy's Law lab kit should be used.
 - Complete the 3 Liver eCRF Modules as information becomes available.

¹ A 'significant' change in the participant's condition refers to a clinically relevant change in any of the individual liver biochemistry parameters (ALT, AST or TBL) in isolation or in combination, or a clinically relevant change in associated symptoms. The determination of whether there has been a significant change will be at the discretion of the investigator, this may be in consultation with the Study Physician if there is any uncertainty.

E 5 Review and Assessment of Potential Hy's Law Cases

The instructions in this section should be followed for all cases where Potential Hy's Law criteria are met.

As soon as possible after the biochemistry abnormality was initially detected, the Study Physician contacts the investigator to review available data and agree on whether there is an alternative explanation for meeting Potential Hy's Law criteria other than DILI caused by the investigational product, to ensure timely analysis and reporting to health authorities within 15 calendar days from date Potential Hy's Law criteria was met. The sponsor's Global Clinical Lead or equivalent and Global Safety Physician will also be involved in this review together with other subject matter experts as appropriate.

According to the outcome of the review and assessment, the investigator will follow the instructions below.

Where there is an agreed alternative explanation for the ALT or AST and TBL elevations, a determination of whether the alternative explanation is an AE will be made and subsequently whether the AE meets the criteria for an SAE:

- If the alternative explanation is **not** an AE, record the alternative explanation on the appropriate eCRF
- If the alternative explanation is an AE/SAE: update the previously submitted Potential Hy's Law SAE and AE eCRFs accordingly with the new information (reassessing event term; causality and seriousness criteria) following the sponsor's standard processes.

If it is agreed that there is **no** explanation that would explain the ALT or AST and TBL elevations other than the investigational product:

- Send updated SAE (report term 'Hy's Law') according to the sponsor's standard processes.
 - The 'Medically Important' serious criterion should be used if no other serious criteria apply
 - As there is no alternative explanation for the Hy's Law case, a causality assessment of 'related' should be assigned.

If, there is an unavoidable delay, of over 15 calendar days in obtaining the information necessary to assess whether or not the case meets the criteria for Hy's Law, then it is assumed that there is no alternative explanation until such time as an informed decision can be made:

- Provides any further update to the previously submitted SAE of Potential Hy's Law, (report term now 'Hy's Law case') ensuring causality assessment is related to investigational product and seriousness criteria is medically important, according to CSP process for SAE reporting.

- Continue follow-up and review according to agreed plan. Once the necessary supplementary information is obtained, repeat the review and assessment to determine whether Hy's Law criteria are still met. Update the previously submitted Potential Hy's Law SAE report following CSP process for SAE reporting, according to the outcome of the review and amending the reported term if an alternative explanation for the liver biochemistry elevations is determined.

E 6 Laboratory Tests

Hy's Law lab kit for central laboratories	
Additional standard chemistry and coagulation tests	GGT
	LDH
	Prothrombin time
	INR
Viral hepatitis	IgM anti-HAV
	IgM and IgG anti-HBc
	HBsAg
	HBV DNA ^a
	IgG anti-HCV
	HCV RNA ^a
	IgM anti-HEV
Other viral infections	HEV RNA
	IgM & IgG anti-CMV
	IgM & IgG anti-HSV
Alcoholic hepatitis	IgM & IgG anti-EBV
	Carbohydrate deficient transferrin
Autoimmune hepatitis	Antinuclear antibody
	Anti-Liver/Kidney Microsomal Ab
	Anti-Smooth Muscle Ab
Metabolic diseases	alpha-1-antitrypsin
	Ceruloplasmin
	Iron
	Ferritin
	Transferrin
	Transferrin saturation

^a HCV RNA; HBV DNA are only tested when IgG anti-HCV is positive or inconclusive
Ab, antibody; anti-CMV, antibody to the cytomegalovirus; anti-EBV, antibody to the Epstein-Barr virus; anti-HAV, antibody to the hepatitis A virus; anti-HBc, antibody to the hepatitis B core antigen; anti-HCV, antibody to the hepatitis C virus; anti-HEV, antibody to the hepatitis E virus; anti-HSV, antibody to the herpes simplex virus; GGT, Gamma-glutamyltransferase; HBV DNA, hepatitis B virus deoxyribonucleic acid; HBsAg, hepatitis B surface antigen; HCV RNA, hepatitis C virus ribonucleic acid; HEV RNA, hepatitis E virus ribonucleic acid; INR, international normalized ratio; IgG, immunoglobulin G; IgM, immunoglobulin M; LDH, lactic acid dehydrogenase

E 7 References

Aithal et al 2011

FDA Guidance for Industry 2009

FDA Guidance for Industry (issued July 2009). Drug-induced liver injury: Premarketing clinical evaluation. [cited 28Oct2021]. Available from <https://www.fda.gov/regulatory-information/search-fda-guidance-documents/drug-induced-liver-injury-premarketing-clinical-evaluation>.

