5.2 Exclusion Criteria

Participants are excluded from the study if any of the following criteria apply:

- 1 History of any clinically important disease or disorder which, in the opinion of the investigator, may either put the participant at risk because of participation in the study, or influence the results or the participant's ability to participate in the study.
- 2 Percutaneous coronary intervention or diagnostic angiogram planned after screening Visit 1. Eligible participants who have a diagnostic angiogram performed in the absence of undergoing a new PCI may continue screening after the diagnostic angiogram has been performed or may be rescreened (Section [5.4](#)).
- 3 History of or planned coronary artery bypass grafting.

- 4 Documented episode of post-MI pericarditis (eg, Dressler's Syndrome) in the 3 months before enrollment.
- 5 Ongoing New York Heart Association Class IV (severe) HF.
- 6 Increased risk of bleeding
 - (a) Patients with history or presence of any bleeding disorder.
 - (b) Signs of ongoing bleeding at screening (eg, identified macroscopic bleeding, low hemoglobin presumed to be caused by bleeding) or high risk for major bleeding in accordance with the Investigator's assessment.
 - (c) Need for chronic therapeutic anticoagulation therapy anticipated to be required throughout the course of the study (short-term treatment with prophylactic doses of heparin/low molecular weight heparin are allowed).
 - (d) Known severe liver disease (eg, ascites and/or clinical signs of coagulopathy).
- 7 History or presence of any of the following:
 - (a) Ongoing infection or febrile illness that in the opinion of the investigator may be the cause of elevated hs-CRP on screening (Visit 1).
 - (b) Ongoing atrial fibrillation or flutter.
 - (c) Cancer within 5 years before randomization (Day 1; Visit 3), with the exception of non-melanoma skin cancer.
 - (d) Alcohol or substance abuse within 6 months before randomization (Day 1; Visit 3), as judged by the investigator.
 - (e) Known history of hypersensitivity reactions to other biologics, to human IgG preparations, or to any component of MEDI6570, or ongoing severe allergy as judged by the investigator.
 - (f) Patients with active positive results on screening for serum hepatitis B surface antigen, hepatitis C antibody, or HIV.
- 8 Any clinically important abnormalities in clinical chemistry, hematology, coagulation parameters, as judged by the investigator, including but not limited to:

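### In the Hy's Law laboratory kit (Protocol Appendix E 6), footnote a makes HBV DNA depend only on the hepatitis C antibody and on no hepatitis B marker: wrong as written, minor.

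*Protocol*

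**What the plan says.** The kit table in Protocol Appendix E 6 has a viral hepatitis block. Two of its entries, HBV DNA and HCV RNA, carry superscript a. The footnote reads: "HCV RNA; HBV DNA are only tested when IgG anti-HCV is positive or inconclusive". The hepatitis B serology entries, HBsAg and "IgM and IgG anti-HBc", carry no footnote. Nor does HEV RNA, another viral nucleic-acid test in the block.

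Three other parts of Appendix E bear on how the kit is used:

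- E 2 defines Hy's Law by the absence of any other reason "to explain the combination of increases, eg, elevated ALP indicating cholestasis, viral hepatitis, another drug".
- E 4.2 has the investigator look into the cause with the Study Physician. "This includes deciding which of the tests available in the Hy's Law lab kit should be used". The same section has them agree an approach to "follow-up (including any further laboratory testing) and the continuous review of data".
- E 5 has the Study Physician and investigator "agree on whether there is an alternative explanation for meeting Potential Hy's Law criteria other than DILI caused by the investigational product", joined by the sponsor's clinical lead and safety physician.

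At entry, criterion 7(f) in Section 5.2 excludes "Patients with active positive results on screening for serum hepatitis B surface antigen, hepatitis C antibody, or HIV". It does not name anti-HBc.

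**The concern.** HBV DNA is a hepatitis B assay, and a result that points to hepatitis B is the natural reason to run it. The footnote gives it one trigger, the hepatitis C antibody, and contains no 'respectively' or second clause from which a hepatitis B trigger could be read. Criterion 7(f) also means that enrolled participants have been screened for the absence of an active positive on that one trigger, so the stated condition would seldom be met.

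What is at stake is the quality of one safety judgement. A case becomes Hy's Law only if no alternative explanation is found, and viral hepatitis is a named alternative. A rule that withholds a hepatitis B assay when hepatitis B serology is positive takes relevant information away from that judgement, or delays it.

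**Working it through.** This is a check of text; the plan states no figure to reproduce and the documents give no rate to compute.

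**Step 1. Is the wording real?** The superscript on the HBV DNA row and the naming of HBV DNA in the footnote agree with each other. That rules out a PDF-reading fault or a redaction as the explanation. The footnote is in the current Appendix E and is not amendment-log text.

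**Step 2. Is there another rule for HBV DNA?** The rest of Appendix E, Protocol Sections 8.2.4 and 8.3.6, and the SAP laboratory sections (3.3.5.2 and 4.2.10.8) contain none. No hepatitis B marker is linked to HBV DNA anywhere in either document.

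**Step 3. Count.** Entries carrying footnote a: 2. Triggers named: 1 (IgG anti-HCV). Hepatitis B serology entries in the kit: 2. Of these, entries that trigger HBV DNA: 0 of 2.

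**Step 4. Apply the rule to each serology pattern in a Potential Hy's Law case.**

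| HBsAg or anti-HBc | IgG anti-HCV | HBV DNA from kit, as written | HBV DNA from kit, split footnote |
|---|---|---|---|
| positive | negative | not run by default | run |
| positive | positive or inconclusive | may be run | run |
| negative | positive or inconclusive | may be run | not triggered |
| negative | negative | not run | not triggered |

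The two versions differ in rows 1 and 3, where a hepatitis B trigger and a hepatitis C trigger give opposite answers.

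**Step 5. Who could fall in row 1?** Criterion 7(f) removes active HBsAg positives at screening, so an HBsAg-positive case would generally need a result that appeared on study. A participant who is anti-HBc positive and HBsAg negative is not excluded by 7(f). Row 3 would likewise generally need a new positive or inconclusive anti-HCV result on study, and would cost only an unneeded assay.

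**Step 6. What happens when information is missing?** Under E 4.2 a Potential Hy's Law case is first reported as an SAE with causality recorded as related. Under E 5, if an unavoidable delay in the information needed runs past 15 calendar days, the absence of an alternative explanation is assumed and the case is updated as Hy's Law, again as related. E 5 then allows the term to be revised once the information arrives. Missing or late evidence therefore leans towards the drug, at least provisionally.

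**The case against.** The strongest reply is that little is lost in practice, and most of it stands.

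The footnote governs one assay within the central kit. E 4.2 is wider: choosing kit tests is only part of the investigation, and further laboratory testing can be agreed. E 1 accepts laboratory data from all sources, local ones included, when determining Hy's Law events. The two hepatitis B serology entries are unconditional, and a positive result would reach experienced reviewers, who could accept hepatitis B as the explanation from serology alone. Criterion 6(d), "Known severe liver disease (eg, ascites and/or clinical signs of coagulopathy", and criteria 8(a) to (c) on AST, ALT and bilirubin also remove participants with evident liver problems at entry. The operative reflex rule may sit in laboratory instructions that are not among the documents, and it may be correct there.

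A reader might infer that a participant with positive hepatitis B serology can get no HBV DNA at all, or that hepatitis B would go undetected. The documents do not support either reading, for the reasons just given. A reader might also infer that attribution is always pushed towards the drug. The defaults lean that way, but reviewers remain free to accept hepatitis B without HBV DNA, so the direction in an individual case is open.

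One part of the reply does not stand. Discretion under E 4.2 does not correct the footnote. The footnote is worded as a restriction on the same kit, and E 4.2 does not say that it may be set aside. Staff or a laboratory following it literally would not run HBV DNA from the kit on a hepatitis B signal alone.

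**Conclusion.** The rule is wrong as written, and the matter is minor. HBV DNA from the kit is tied to the wrong virus's antibody and to 0 of the 2 hepatitis B serology entries. The consequence is confined to the E 5 review of alternative explanations. It could enter reported data only through the term and causality assigned to an individual SAE. The SAP liver summaries in Section 4.2.10.8 use ALT, AST, bilirubin and ALP, so they do not change, and neither do the efficacy analyses, sample size or error rates.

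Confidence is high for the wording. For the consequence, the conclusion assumes that the footnote is followed literally and that the central laboratory's instructions do not already differ from it. The number of cases affected cannot be determined: it needs a Potential Hy's Law case with the row 1 serology, and the documents give a frequency for neither.

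**What to change.** Replace footnote a with two footnotes:

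- (a), on HCV RNA: run only if IgG anti-HCV is positive or inconclusive.
- (b), on HBV DNA: run if HBsAg or anti-HBc (IgM or IgG) is positive or inconclusive.

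The hepatitis B entries that trigger HBV DNA then go from 0 of 2 to 2 of 2. Then confirm that the central laboratory's instructions say the same. The cost is one edited footnote, one check with the laboratory, and an occasional extra run of an assay that is already in the kit.
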